**Table 8. Dose Modification Guidelines for Study Drug-Related Adverse Events**

Dose Interruption	
Event	Recommended Action
Grade 3 or higher AE that is (1) study -drug related in the opinion of the Investigator AND (2) that precludes continued dosing at the current dose level due to safety concern or lack of tolerability (in the Investigator's judgment)	Study Drug: May be held for 10 days. If, in the opinion of the Investigator, a Grade 3 AE has resolved to $\leq$ Grade 1, participant may resume daily dosing of study drug at a lower dose (not lower than 100 mg) or continue with the original dose or a lower daily dose.  Maximum dose hold is 28 continuous days. If, in the opinion of the Investigator, a longer dose hold is clinically needed, the Medical Monitor should be consulted.
ALT $\geq 3X$ ULN if ALT WNL at baseline OR $>3X$ ULN AND a $\geq 2$ -fold increase above baseline values if elevated ALT values at baseline  In the absence of additional signs of compromised liver function such as elevated PT, aPTT, INR, elevated conjugated bilirubin, jaundice, or hepatic pain.	Study drug: Confirm by repeat testing within 48 to 72 hours if possible and then repeat liver panel at least weekly until ALT levels improve.  Additional Actions: If ALT levels continue to increase hold the study drug for 10 days and notify the Medical Monitor.  Upon resolution of the elevated ALT, the participant may resume daily dosing of study drug at the original dose or a lower dose.
ALT $\geq 5X$ and $<8X$ ULN (confirmed by repeat testing within 48 to 72 hours)  In the absence of additional signs of compromised liver function such as elevated PT, aPTT, INR, elevated conjugated bilirubin, jaundice, or hepatic pain.	Study drug: Hold the study drug for 10 days.

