#### **9.4.3. Severity of Adverse Events**

Whenever possible, the severity of all AEs will be graded using the National Cancer Institute Common Terminology Criteria for Adverse Events (NCI CTCAE), Version 5.0.

For AEs not adequately addressed in the NCI CTCAE, Version 5.0, the criteria presented in [Table 11](#) should be used.

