#### 11.5.4. Adverse Event Grading for Kidney Safety Laboratory Abnormalities

AE grading for decline in kidney function (ie, eGFR or eCrCl) will be according to CTCAE criteria for both pediatric and adult participants.

CTCAE Term (2017)	Grade 1	Grade 2	Grade 3	Grade 4	Grade 5
AKI	NA	NA	Hospitalization indicated	Life-threatening consequences; dialysis indicated	Death
AKI: A disorder characterized by acute loss of kidney function (within 2 weeks) and is traditionally classified as pre-renal (low blood flow into kidneys), renal (kidney damage), or post-renal causes (ureteral or bladder outflow obstruction).					
Creatinine increased	>ULN to 1.5 x ULN	>1.5 to 3.0 x baseline OR >1.5 to 3.0 x ULN	>3.0 to 6.0 x baseline OR >3.0 to 6.0 x ULN	>6.0 x ULN	NA
CKD	eGFR $\geq 60$ to 89 mL/min/1.73m  OR eCrCl $\geq 60$ to 80 mL/min	eGFR 30 to 59 mL/min/1.73m  OR eCrCl 30 to 59 mL/min	eGFR 15 to 29 mL/min/1.73m  OR eCrCl 15 to 29 mL/min	eGFR <15 mL/min/1.73m  OR eCrCl <15 mL/min OR dialysis indicated	Death
Proteinuria	ADULTS: Proteinuria 1+ OR Proteinuria >0.5 to <1.0 g/24 h	ADULTS: Proteinuria 2+ or 3+ OR Proteinuria 1.0 to <3.5 g/24 h PEDIATRICS: Urine Protein-	ADULTS: Proteinuria 4+ OR Proteinuria $\geq 3.5$ g/24 h PEDIATRICS: Urine Protein-to-Creatinine	NA	NA

CTCAE Term (2017)	Grade 1	Grade 2	Grade 3	Grade 4	Grade 5
		to-Creatinine Ratio (UPCR) 0.5 to 1.9	Ratio (UPCR) >1.9		

CKD: A disorder characterized by gradual and usually permanent loss of kidney function resulting in kidney failure.

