**2.2.3. Study Design**

C5351005 (OLE) is designed as a multicenter, global, open-label extension study. The primary objective is to assess the long-term safety of osivelotor in participants with SCD. This study is available to eligible participants who have previously enrolled in a Pfizer-sponsored osivelotor clinical study and meet the entry criteria for this study.

Eligible participants will receive open-label osivelotor at Baseline (Day 1). It is intended that Day 1 coincides with the final visit from the originating osivelotor study. End of Treatment (EOT) assessments from the originating study will serve as Baseline assessments for this study. If Day 1 for this study is greater than 7 days from the completion of the originating study, new baseline assessments will be obtained. If during the period between Day 1 of this study and completion of the originating study no dose is received for greater than 3 consecutive days, an appropriate loading dose will be administered prior to continued maintenance dosing.

Only participants from C5351004 Part A (also referred to as the “parent study”) were enrolled into the OLE. C5351004 Part A is a study which enrolled only adult participants. There are two sets of participants rolling over from C5351004 Part A to the OLE study – (i) participants without a delayed start (Date of first dose in C5351005 – EOT date from C5351004 + 1 ≤ 42 days) and (ii) participants with a delayed start of OLE (Date of first dose in C5351005 – EOT date from C5351004 + 1 > 42 days). Each set follows a distinct schedule of assessments as outlined in the C5351005 protocol.

**3. ENDPOINTS AND BASELINE VARIABLES: DEFINITIONS AND CONVENTIONS****3.1. Primary Endpoint(s)****3.1.1. Incidence of TEAEs**

A treatment-emergent adverse event (TEAE) is defined as an AE that occurs during the effective duration of treatment defined as the time from the first dose of study drug through last dose of study drug + 56 days.

TEAEs that occur in the parent study are not counted as TEAEs in this study. In case, the start date of AE is the same date as the treatment start date and the question in the AE CRF page “Is this AE continuing from the parent study?” = “Yes”, then the event is not a TEAE,

as long as it can be confirmed that the AE in question had a start date in the parent study and no end date in the parent study.

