#### 6.1.1. Incidence of TEAEs

AEs will be mapped to system organ class (SOC) and preferred term using the Medical Dictionary for Regulatory Activities (MedDRA).

The following guidelines will be used to capture the different types of TEAEs based on the AE CRF:

- **Treatment-Related Adverse Events:** adverse events with relationship to study treatment (as recorded on the AE eCRF page, Relationship with study treatment = Related) reported by the investigator and those of unknown relationship (i.e., no answer to the question 'Relationship with study treatment').
- **Serious Adverse Events (SAE):** serious adverse events (as recorded on the AE eCRF page, Was the AE Serious = Yes).
- **Non-Serious Adverse Events:** non-serious adverse events (as recorded on the AE eCRF page, Was the AE Serious = No).
- **Adverse Events Leading to Interruption of Study Treatment:** adverse events leading to interruption of study treatment (as recorded on the AE eCRF page, Action taken with study treatment = Drug interrupted).
- **Adverse Events Leading to Dose Reduction:** adverse events leading to dose reduction (as recorded on the AE eCRF page, Action taken with study treatment = Dose Reduced).
- **Adverse Events Leading to Discontinuation of Study Treatment:** adverse events leading to discontinuation of study treatment (as recorded on the AE eCRF page, Action taken with study treatment = Drug Permanently Discontinued).
- **Adverse Events Leading to Death:** adverse event leading to death (as recorded on the AE eCRF page, Did the AE result in Death = Yes, as well as AEs of Grade 5).

TEAEs leading to study discontinuation will be derived based on the response to the following question in the AE CRF form: "Caused Study Discontinuation"

The overall incidence of TEAEs will be summarized (Section 5.3). This table includes: TEAEs (number of TEAEs and participants with TEAEs),

Number of participants with:

- TEAEs by maximum severity,
- Treatment-related TEAE,
- Treatment-related TEAE by maximum severity,
- Treatment emergent SAE,
- Treatment-related treatment emergent SAE,
- Treatment emergent non-serious AE,
- TEAEs leading to study discontinuation,
- TEAEs leading to study treatment discontinuation,

TEAEs leading to study treatment interruption,  
TEAEs leading to dose reduction,  
TEAEs leading to death.

The TEAEs will be summarized and tabulated at participant level using counts and percentages:

- TEAEs by SOC and PT
- TEAEs by SOC, PT and maximum reported severity

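### The creatinine row of the kidney grading table is not monotone: with a baseline below 0.5 x ULN, a band of rises above 6-fold is graded lower than a 4-fold rise

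*Protocol*

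**What the plan says.** Protocol Section 9.4.3 makes NCI CTCAE version 5.0 the general scale: "the severity of all AEs will be graded using the National Cancer Institute Common Terminology Criteria" for Adverse Events. Section 11.5.4 then prints its own kidney table and says that grading of a decline in kidney function "will be according to CTCAE criteria for both pediatric and adult participants". The Creatinine increased row reads:

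- Grade 1: ">ULN to 1.5 x ULN"
- Grade 2: ">1.5 to 3.0 x baseline OR >1.5 to 3.0 x ULN"
- Grade 3: ">3.0 to 6.0 x baseline OR >3.0 to 6.0 x ULN"
- Grade 4: above 6.0 x ULN, with no baseline clause
- Grade 5: not applicable

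No footnote or other section says how to grade a rise above 6.0 x baseline that is still at or below 3.0 x ULN.

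The grade is used in two places. The first dose-interruption row of Protocol Table 8 concerns a "Grade 3 or higher AE that is (1) study -drug related in the opinion of the Investigator" that also prevents continued dosing. SAP Section 6.1.1 tabulates the primary safety endpoint as "TEAEs by SOC, PT and maximum reported severity".

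**The concern.** A severity scale should never assign a lower grade to a larger abnormality in the same person. Here the baseline clause of Grade 3 ends at 6.0 and Grade 4 does not take it over. For a participant who starts with low creatinine, six times baseline can still be well under 3.0 x ULN. The value then leaves Grade 3 from above and lands in a ULN clause that belongs to Grade 2 or Grade 1.

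At stake is the count of Grade 3 or higher kidney events in a study whose primary objective is long-term safety, together with one of the conditions in a Table 8 row. There is also a consistency problem. A site that follows the row literally and a site that uses judgment would grade the same value differently.

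**Working it through.** **Inputs.** The four cut-offs come from Section 11.5.4. The documents give neither a creatinine ULN nor a baseline distribution. The algebra therefore uses ratios, and mg/dL examples rest on an assumed ULN. Where two clauses point to different grades, the higher one is taken.

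**Notation.** Let r = baseline / ULN and f = new value / baseline. Then new value / ULN = f x r.

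**Step 1: a 4-fold rise.** f = 4 lies between 3.0 and 6.0, so the Grade 3 baseline clause is met whatever r is. A 4-fold rise is always at least Grade 3.

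**Step 2: a rise above 6-fold.** With f > 6 no baseline clause applies, so only f x r counts. The grade is below 3 when f x r <= 3.0, that is, f <= 3/r. Combined with f > 6 this needs 3/r > 6, so r < 0.5. The under-graded band is 6 < f <= 3/r. At r of 0.5 or more it is empty.

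**Step 3: numbers.**

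| r | 4-fold rise | 6.5-fold rise: f x r | Grade at 6.5-fold | Band ends at f = 3/r |
|---|---|---|---|---|
| 0.15 | Grade 3 | 0.975 | none | 20 |
| 0.20 | Grade 3 | 1.30 | 1 | 15 |
| 0.25 | Grade 3 | 1.625 | 2 | 12 |
| 0.30 | Grade 3 | 1.95 | 2 | 10 |
| 0.40 | Grade 3 | 2.60 | 2 | 7.5 |
| 0.45 | Grade 3 | 2.925 | 2 | 6.67 |
| 0.50 | Grade 3 | 3.25 | 3 | no band |
| 0.80 | Grade 3 | 5.20 | 3 | no band |
| 1.00 | Grade 3 | 6.50 | 4 | no band |

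A grid scan over r from 0.05 to 1.50 and f from just above 6 to 30 found an inversion at every r below 0.5 and at none from 0.5 upward.

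**Step 4: in mg/dL, assuming ULN = 1.2.**

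- Baseline 0.4: 4 x 0.4 = 1.6 (1.33 x ULN) is Grade 3; 6.5 x 0.4 = 2.6 (2.17 x ULN) is Grade 2. The band runs from above 6 x 0.4 = 2.4 to 3 x 1.2 = 3.6, which is 6 to 9 times baseline.
- Baseline 0.5: 2.0 is Grade 3; 3.25 (2.71 x ULN) is Grade 2. The band runs from above 3.0 to 3.6, which is 6 to 7.2 times baseline.
- For an assumed ULN of 1.0 to 1.3, the inversion can occur at baselines below 0.50 to 0.65.

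**Step 5: does the CKD row of the same table catch these values?** It reaches Grade 3 when eGFR falls below 30. With the creatinine-only equation of Section 11.5.2.1, a 30-year-old man at 2.6 mg/dL has 142 x (2.6/0.9)^-1.200 x 0.9938^30 = 33.0, which is CKD Grade 2. At that age and a baseline of 0.4, values up to about 2.81 mg/dL stay at Grade 2 on both rows. For women at either baseline, and for men at baseline 0.5, eGFR at age 18 is already below 30 where the band begins: 29.0 for a woman at 2.41 mg/dL and 29.8 for a man at 3.01 mg/dL. It falls further with age and with higher creatinine. On these examples, the CKD row covers much of the band but not all of it.

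**Step 6: effect of dropping the 6.0 limit on the Grade 3 baseline clause.** The baseline clauses then give 0, 2, 3 as f rises, and the ULN clauses give 0, 1, 2, 3, 4. Both sequences never fall, so the higher of the two never falls. The same grid scan found no remaining inversion.

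**The case against.** The best opposing case accepts the arithmetic and disputes the consequences. Most of that case stands.

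- **Only a middle band is affected.** A reader might infer that every rise above 6-fold, or the most severe kidney events as a class, is recorded as moderate. The table does not support that: above 3.0 x ULN Grade 3 returns, and above 6.0 x ULN Grade 4 applies.
- **Other recording rules may take over.** Sections 9.4.7.1 and 9.4.7.2 have the diagnosis recorded in place of the laboratory sign. Section 8.2.1 starts a kidney work-up at far smaller rises. An event recorded as AKI is graded on the AKI row, which starts at Grade 3, though only if hospitalization is indicated. The CKD row may also give Grade 3, although it describes gradual loss and may not suit an acute rise.
- **Table 8 does not turn on grade alone.** A reader might infer that these participants lose the dose-interruption safeguard. That row also requires relatedness and that the event preclude dosing at the current level. Sections 7.5, 8.2 and 8.2.2 leave room to act without any grade threshold.
- **The SAP keeps the worst recorded grade.** An event caught at Grade 3 on the way up stays Grade 3. This is only partial protection: under Protocol Table 2, participants without a delayed start have scheduled chemistry every 12 weeks, so the intermediate value may never be seen.
- **Reach is limited.** SAP Section 2.2.3 says that only Part A participants entered and that "C5351004 Part A is a study which enrolled only adult participants", so a pediatric effect on the final data is theoretical.

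An investigator might also assign Grade 3 regardless. None of this repairs the row; it limits how often the flaw will show in the results.

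**Conclusion.** The row is wrong as written. For a baseline below 0.5 x ULN, a rise above 6-fold and up to 3/r-fold is Grade 2 or lower, while a 4-fold rise is Grade 3. This follows from the printed cut-offs alone and needs no outside knowledge of CTCAE.

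The practical size is probably small and cannot be computed: the documents give no ULN and no baseline creatinine distribution, and they show no affected participant. The mg/dL figures depend on an assumed ULN of 1.2, with 1.0 to 1.3 as the range. The documents also do not show whether sites graded from this table or from CTCAE itself. The point justifies a correction and a check of recorded events. It does not show that the Grade 3 or higher counts are materially wrong, nor that a dose-interruption rule has failed.

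**What to change.** Reconcile the Creatinine increased row in Section 11.5.4 with the CTCAE version 5.0 that Section 9.4.3 names, so that the grade cannot fall as creatinine rises. Removing the 6.0 upper limit from the Grade 3 baseline clause would achieve this, subject to that comparison.

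Before the primary analysis, which the SAP places after all participants have completed or left the study, list recorded creatinine adverse events with a value above 6.0 x baseline and check each grade. Because the SAP tabulates reported severity, raise any discrepancy as a site query; do not overwrite the grade in programming.

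The cost is one table cell and one programmed listing. The downside is that a few events may move from Grade 2 or lower to Grade 3.

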#### 11.6. Appendix 4: Prohibited and Restricted Concomitant Medications That May Result in DDI

The prohibited concomitant medications listed below (Table 17) should not be taken with osivelotor for the period of time at least equal to the required washout period listed in the table and throughout the conduct of the study. Restricted concomitant medications may be used but with the following restrictions (Table 18).

The Pfizer study team is to be notified of any prohibited or restricted medications taken during the study. After consulting with the sponsor, the investigator will make a judgment on the ongoing participation of any participant with prohibited or restricted medication use during the study.

This list of drugs prohibited and restricted for potential DDI concerns with the IMP may be revised during the course of the study with written notification from the sponsor to include or exclude specific drugs or drug categories for various reasons (eg, emerging DDI results for the IMP, availability of new information in literature on the DDI potential of other drugs) if the overall benefit/risk assessment is not impacted or if the changes do not significantly impact the safety of participants or the scientific value of the trial.

This is not an all-inclusive list. Site staff should consult with the sponsor or designee with any questions regarding potential DDI.

**Table 17. Examples of Prohibited Concomitant Medications**

Drug Category	Drugs	Washout Period Requirement Prior to First Dose of Osivelotor
Herbal Preparations and Dietary Supplements	Preparations obtained by subjecting herbal substances to treatments such as extraction, distillation, expression, fractionation, purification, concentration or fermentation. Note: prescription or nonprescription vitamins are an exception	14 days prior to first dose of osivelotor
CCI		5 elimination half-lives or 14 days, whichever is longer

**Table 17. Examples of Prohibited Concomitant Medications**

Drug Category	Drugs	Washout Period Requirement Prior to First Dose of Osiveltor
CCI		
		5 elimination half-lives or 14 days, whichever is longer
		5 elimination half-lives or 14 days, whichever is longer
Prohibited Juices	Participants are not permitted to consume grapefruit, grapefruit juice, and/or Seville oranges	14 days prior to first dose of osiveltor

Abbreviations: CCI

Note: This is not an exhaustive list. Country-specific lists may be used if available.

For an updated list, refer to the following link: <https://www.fda.gov/drugs/drug-interactions-labeling/drug-development-and-drug-interactions-table-substrates-inhibitors-and-inducers>.

**Table 18. Examples of Restricted Concomitant Medications**

Drug Category	Drugs	Restrictions
CCI		Osiveltor must be administered at least 4 hours before CCI are administered
		Participants should avoid sensitive CCI. If not possible, consider dose adjustment.
		Use caution with sensitive CCI and consider dose adjustment, as needed.

Abbreviations: CCI

Note: This is not an exhaustive list. Country-specific lists may be used if available.

For an updated list, refer to the following link: <https://www.fda.gov/drugs/drug-interactions-labeling/drug-development-and-drug-interactions-table-substrates-inhibitors-and-inducers>.

Investigators should consult the product label for any other medication used during the study for information regarding medication that is prohibited for concomitant use.

## 11.7. Appendix 5: Protocol Amendment History

The protocol amendment summary of changes table for the current amendment is located directly before the Table of Contents. The protocol amendment summary of changes tables for past amendments can be found below:

### Amendment 3.0 (22 June 2023)

Change	Rationale	Section(s) affected
Removed the personal identifiable information for the sponsor's medical officer from the title page and removed the statement of approval and compliance	Per pfizer protocol templates, there should be no personal identifiable information in the protocol. That information will be documented separately.	Title page Statement of approval and compliance
Increased the number of study sites to approximately 60 globally	For consistency with the number of sites in the originating studies	Synopsis
Added promis sf-fatigue 13a, promis sf-pain interference 8a, promis numeric rating scale-pain intensity, euroqol eq-5d-5l, and work productivity and activity impairment assessments to the quality-of-life assessments	This information is being collected in the originating study (gbt021601-021) and will continue to be collected in the open-label extension study to monitor patient reported outcomes	Synopsis Schedule of assessments and procedures Section 3 Section 8.8
Added specific detail that the pgi-c and pgi-s assessments will be for fatigue and pain, and that the cgi-c and cgi-s assessments will be for scd	For consistency with the originating study	Synopsis Schedule of assessments and procedures Section 3 Section 8.8
Revised the outcome measure of "trough and 1- to 2-hour blood and plasma concentrations" to "blood and plasma concentrations"	To provide for assessment of pk at various time points as outlined in the schedule of assessments	Synopsis Schedule of assessments and procedures Section 3
Added that events representing scd-related complications such as vaso-occlusive crisis (voc), (ie, acute chest syndrome (acs), hepatic sequestration, splenic sequestration, priapism, and dactylitis) will also be reported as measures of efficacy	For clarity on the measures of efficacy	Synopsis Section 8.2
Removed the criteria that if the day 1 visit does not occur on the same day as the end of treatment visit from the originating study, the day 1 visit must occur within 30 calendar days of completion of the originating study	There have been site activation delays that limited the ability of participants to enroll in the open label extension study so in order to allow those participants to	Synopsis Schedule of assessments and procedures Section 4.1

Change	Rationale	Section(s) affected
	continue on study drug, the 30-day window is being removed	Section 5.1
Added that if during the period between day 1 of this study and completion of the originating study, no dose is received for greater than 3 consecutive days, an appropriate loading dose should be administered prior to continued maintenance dosing	Blood concentration of drug will drop below steady state levels following a gap in dosing. In order to bring participants back up to steady state levels (the therapeutic window), a new loading dose will be administered	Synopsis Section 2.2 Section 4.1 Section 4.3 Appendix 1
Added a visit at week 1 (the end of the loading dose period) for participants with a gap in dosing >42 consecutive days from completing the originating study	To dispense new study drug and switch from the loading dose to the maintenance dose	Synopsis Schedule of assessments and procedures Section 4.1 Section 8.2
Added to the inclusion criteria 1 that participants who completed treatment from the originating study but were not able to rollover into study gbt021601-022 due to a delay in study site activation will be eligible provided other eligibility criteria are met	For consistency with the removal of the requirement to have been on the previous study within 30 calendar days	Synopsis Section 5.1
Revised the pregnancy testing to be a urine test at baseline unless there is a delay in start of ole of >7 days (in which case a serum pregnancy test would be administered)	To clarify that serum pregnancy tests are only required if there is a gap of >7 days in start of ole or to confirm a positive urine test	Schedule of assessments and procedures
Added a qualitative interview to the quality-of-life measurements which will be conducted with participants by telephone or online/web conference at the baseline visit	To collect data regarding participants' disease- and treatment-related experiences	Schedule of assessments and procedures Section 8.8
Added that additional nonclinical information can be found in the investigator brochure	For clarity on where to find more information	Section 2.1
Updated the clinical experience section	To provide more up to date information on the clinical studies	Section 2.1
Added individual level stopping rules for participants rolling over from the 200 mg treatment arm from part a of study gbt021601-021	For consistency with the originating study	Section 6.5.1
Revised the language in the treatment of overdose	For consistency with pfizer processes	Section 6.6

Change	Rationale	Section(s) affected
Added a table with examples of prohibited or restricted concomitant medications	For clarity	Section 6.7.1 table 9
Added a section regarding environmental exposure, exposure during pregnancy or breastfeeding, occupational exposure, and medication errors	For consistency with pfizer processes and for additional clarify	Section 8.4.13 Section 8.4.13.1 Section 8.4.13.2 Section 8.4.13.3 Section 8.4.14
Added to the outcome measures "it is intended that day 1 coincides with the final visit from the originating gbt021601 study. End of treatment (eot) assessments from the originating study will serve as baseline assessments for this study. If day 1 for this study is greater than 7 days from the completion of the originating study, new baseline assessments will be obtained. Additional assessments that may not have been included in the prior eot assessments are outlined in the schedule of assessments and will need to be completed prior to study drug administration."	To clarify that there are two potential baseline assessments (either from the originating study, or at the start of the ole)	Section 9.2.1
Added a section on reporting of safety issues and serious breaches of protocol	For consistency with pfizer processes and for additional clarify	Section 10.1.3
Revised the informed consent process, data protection, dissemination of clinical study data, data quality assurance, study and site start and closure, publication policy, sponsor's medically qualified individual	For consistency with pfizer template language and processes	Section 10.1.4 Section 10.1.5 Section 10.1.6 Section 10.1.7 Section 10.1.8 Section 10.1.9 Section 10.1.10
Updated appendix 1 guidelines for dose for participants rolling over with a gap in dosing	For additional clarity on dose information	Appendix 1
Added appendix 2 on liver safety	To provide guidance on monitoring, reporting, and managing potential drug-induced liver injury	Appendix 2

Abbreviations: pgi-c, patient global impression of change; pgi-s, patient global impression of severity; promis, patient-reported outcome measurement information system; scd, sickle cell disease; sf, short form.

